8.2 PARTICIPANT DISCONTINUATION/WITHDRAWAL FROM THE STUDY

Participants are free to withdraw from participation in the study at any time upon request.

An investigator may discontinue or withdraw a participant from the study for the following reasons:

- Pregnancy
- Significant study intervention non-compliance
- If any clinical adverse event (AE), laboratory abnormality, or other medical condition or situation occurs such that continued participation in the study would not be in the best interest of the participant
- Disease progression which requires discontinuation of the study intervention
- If the participant meets an exclusion criterion (either newly developed or not previously recognized) that precludes further study participation
- Participant unable to receive study intervention for 1 infusion period

The reason for participant discontinuation or withdrawal from the study will be recorded on the Study Closeout/Withdrawl/Termination CRF. Participants who sign the informed consent form and are randomized but do not receive the study intervention may be replaced.

8.3 LOST TO FOLLOW-UP

A participant will be considered lost to follow-up if he or she fails to return for 2 scheduled visits and is unable to be contacted by the study site staff.

The following actions will be taken if a participant fails to return to the clinic for a required study visit:

- The study coordinator will attempt to contact the participant and reschedule the missed visit within the 10 day window between pegloticase infusions and counsel the participant on the importance of maintaining the assigned visit schedule and ascertain if the participant wishes to and/or should continue in the study.
- Before a participant is deemed lost to follow-up, the investigator or designee will make every effort to regain
 contact with the participant. These contact attempts should be documented in the participant's medical record
 or study file.

- Should the participant continue to be unreachable, he or she will be considered to have withdrawn from the study with a primary reason of lost to follow-up.
- Based on our competitive enrollment of this study in the event a participant is lost to follow-up, withdraws
 consent and discontinues the study before the end of week 12 and is therefore unable to contribute to the
 primary outcome, the enrolling site will be afforded the opportunity to enroll a replacement participant.

9 STUDY ASSESSMENTS AND PROCEDURES

This study will be coordinated by the University of Alabama at Birmingham (UAB). All study visits and procedures will be performed at the United States, at UAB, the University of Michigan, and up to 6 to be named sites. Enrollment will be competitive between sites. Frequency of study visits and clinical evaluations can be found in **Table 1**. Following the first 12 week dual therapy phase, participants will be given an additional three months of open-label pegloticase only therapy (see **Figure 1**) and will be followed to better understand the long-term efficacy (durability) of this approach, which is essential for future studies. Specifically, we will whether assess the durability of the short course of MMF continues over the next 12 weeks in the absence of MMF.

Participants will be seen according to schedule of visits and evaluations outlined in **Table 1** and per the details that follow:

Visit 1 - Screening Visit

The screening visit will take approximately 1 hour to complete. Potential participants will be screened to determine if they satisfy all inclusion and exclusion criteria. Men and women 18 years of age or older will be invited to proceed with informed consent (IC) and enroll in the study. At the screening visit, the study objectives will be explained to potential participants. After all questions raised by a potential participant are answered, and before any protocol-specified screening procedures are initiated, they will be offered the IC for the screening evaluation. A copy of the signed and dated IC form must be provided to the participant. After IC is obtained, a participant number will be assigned. All screening procedures must be completed and eligibility criteria met prior to start of immune-modulating therapy and pegloticase infusions. Basic demographic information and reason(s) for exclusion must be completed on the specified case report form (eCRF) pages for all participants who signed an ICF, but never received pegloticase. During the screening visit, the following procedures will be performed, and information will be obtained to determine eligibility to continue in this research study:

- o Review inclusion/exclusion criteria
- o ICF
- o Date of birth
- Self-reported race/ethnicity
- Medical history that might preclude study participation
- Gout history and symptom severity
- Medication review
 - Medication history (including use of over-the-counter medications [eg. aspirin], use of other prescription medications including gout medications)
 - Dietary supplement/vitamin use
- Vital signs
- Physical exam includes, but is not limited to
 - Eye, Head, Ears, Nose, and Throat Exam (HEENT), and Neck
 - Cardiovascular
 - Dermatological

- Respiratory
- Gastrointestinal
- Musculoskeletal
- Neurologic
- Integumentary
- VS/Measurements
- Gout Flare/ assessment
- o PROs (eg. PROMIS-29 & GIS instrument)
- Blood draw
- Screening Visit Laboratory
 - CBC with diff
 - HIV1 and 2 Antibody Screen
 - IgG
 - sUA
 - Pregnancy test for premenopausal women
 - Comprehensive Metabolic Panel (CMP)
 - G6PD
 - Specimen collection (blood sample for serum banking)
 - Pegloticase Antibody/Mechanistic Study

Vital signs will consist of heart rate, respiratory rate, blood pressure (noting the position in which it was obtained), and body temperature (taken either orally or aurally). All measurements of pulse rate and blood pressure should be made after approximately 5 minutes of rest. Focused history and physical examination: Information collected will include date of birth, self-reported race/ethnicity (defined as in previous studies investigating its role in rheumatic diseases, gout history, medication history (including use of aspirin, gout medications), weight, and height. Assessments for presence of tophi will be conducted as well as gout history and symptom severity.

- Document the number of gout flares in the last 6 months and 12 months and the most recent occurrence. Patients with gout flares can enter the study if the flare treatment is discontinued 1 week prior to the first dose of pegloticase.
- o Document the presence and/or history of gout-related kidney disease.

Physical examinations will be performed by body system at Screening, Visit 11, and Visit 17 (end of treatment) or early termination visit in the pegloticase dosing phase. Significant findings prior to the administration of pegloticase must be recorded in the patient's medical record and included on the Medical History in the eCRFs. Significant findings that occur after administration of pegloticase which meet the definition of an AE must be recorded in the medical record and on the Adverse Events eCRF page.

All women of childbearing potential must use an effective form of birth control during this study and for 30 days after completion of the study. Acceptable methods of birth control include hormonal control methods, inter-uterine device, a double-barrier method (diaphragm with spermicide, condom with spermicide) or abstinence. All male participants will be cautioned to use proper birth control methods with their partners during the course of the study in which MMF is received.³

Laboratory: sUA, CMP, CBC with diff, and pregnancy test for premenopausal women. Additionally, a sample will be collected at screening, Visits 1, 8, 11, 14, and 17-20 for evaluation of anti-pegloticase Ab. Serum samples (see **Appendix 5)** will be collected and prepared for transport to the clinical research lab in the Division of Clinical Immunology and

Rheumatology at the University of Alabama at Birmingham. All lab samples will be discarded if the participant is deemed not eligible for the study.

Visit 2 - Run-In Visit

- Obtain and record vital signs, including pulse rate, sitting blood pressure, and body temperature
- Review / update concomitant medications
- Gout Flare/tophus assessment
- o Blood draw
- Laboratory
 - sUA
 - Urine pregnancy test for premenopausal women
 - CMP
- Randomization will occur at Visit 2/Run-In. Dispense 2 week course of MMF (500mg/twice per day for the first week, and 1000mg/twice per day for the second week of run-in) or placebo, with dosing instructions per randomization assignment.
- Gout Flare Prophylaxis

Participants will be placed on a prophylactic regimen of colchicine or NSAID to prevent gout flares, unless medically contraindicated or not tolerated, and will receive this prophylaxis for at least two weeks prior to the first administration of pegloticase. Gout flare prophylaxis will continue for the duration of the study unless medically contraindicated or not tolerated.

Visit 3 (Baseline-0 weeks)

Visit 3 will occur within 2 weeks of the run-in visit.

The markers for the study primary and secondary outcomes will be collected at each visit. Other data will be collected as needed for safety monitoring.

- Obtain and record vital signs, including pulse rate, sitting blood pressure, and body temperature
- Review / update concomitant medications
- Assess any AEs, and record
- Gout Flare assessment
- Assess compliance (via pill count) and dispense course of MMF (1000 mg/twice per day) or PBO, with dosing instructions
- PROs (PROMIS-29 & GIS instrument)
- Targeted Physical Exam and joint assessment
- Laboratory
 - CBC with diff
 - IgG
 - sUA
 - Pregnancy test for premenopausal women
 - CMP
 - MMF adherence
 - Pegloticase Antibody/Mechanistic Study
- Gout Flare Prophylaxis
- IR Prophylaxis / Assess for IRs
- Administer pegloticase infusion, per site guidelines

In addition to gout flare prophylaxis all participants will receive infusion prophylaxis throughout the study (e.g., fexofenadine (60 mg PO) the night before and fexofenadine (60 mg PO) and acetaminophen (1000 mg) the morning of the infusion; and hydrocortisone (200 mg IV) immediately prior to the infusion).

Visit 4 (1 week)

Participants will report 1 week following Visit 3 for a blood draw and check of their CBC.

- Laboratory
 - CBC with diff
 - sUA
 - MMF adherence

Visit 5 (2 weeks)

- Obtain and record vital signs, including pulse rate, sitting blood pressure, and body temperature
- Targeted Physical Exam
- o Review / update medical history concomitant medications
- o Assess any AEs, and record
- Gout Flare assessment
- Assess compliance (via pill count) and dispense course of MMF (1000 mg/twice per day) or PBO, with dosing instructions
- Laboratory
 - CBC with diff
 - CMP
 - sUA
 - Pregnancy test for premenopausal women
 - MMF adherence
- o Gout Flare Prophylaxis
- Administer pegloticase infusion, per site guidelines
- IR Prophylaxis/ Assess for IRs

Visit 6 (3 weeks)

Participants will report 1 week following Visit 3 for a blood draw and check of their CBC.

- Laboratory
 - CBC with diff
 - MMF adherence

Visit 7 (4 weeks)

- Obtain and record vital signs, including pulse rate, blood pressure, and body temperature
- o Targeted Physical Exam and joint assessment
- Review / update concomitant medications
- Assess any AEs, and record
- Gout Flare assessment
- PROs (PROMIS-29 & GIS instrument)
- Assess compliance (via pill count) and dispense course of MMF (1000 mg/twice per day) or PBO, with dosing instructions
- Laboratory Assessments

- CBC with diff
- CMP
- sUA
- Pregnancy test for premenopausal
- MMF adherence
- Gout Flare Prophylaxis
- IR Prophylaxis /Assess for IRs
- Administer pegloticase infusion, per site guidelines

Visit 8 (6 weeks)

- Obtain and record vital signs, including pulse rate, blood pressure, and body temperature
- Targeted Physical Exam and joint assessment
- Review / update concomitant medications
- Assess any AEs, and record
- o Gout Flare assessment
- Assess compliance (via pill count) and dispense course of MMF (1000 mg/twice per day) or PBO, with dosing instructions
- Laboratory Assessments
 - CBC with diff
 - IgG
 - sUA
 - Pregnancy test for premenopausal women
 - CMP
 - MMF adherence
 - Pegloticase Antibody/Mechanistic Study
- o Gout Flare Prophylaxis
- o IR Prophylaxis / Assess for IRs
- Administer pegloticase infusion, per site guidelines

Visit 9 (8 weeks)

- Obtain and record vital signs, including pulse rate, blood pressure, and body temperature
- Targeted Physical Exam and joint assessment
- o Review / update concomitant medications
- Assess any AEs, and record
- Gout Flare assessment
- PROs (PROMIS-29 & GIS instrument)
- Assess compliance (via pill count) and dispense course of MMF (1000 mg/twice per day) or PBO, with dosing instructions
- Laboratory Assessments
 - CBC with diff
 - CMP
 - sUA
 - Pregnancy test for premenopausal
 - MMF adherence

- Gout Flare Prophylaxis
- o IR Prophylaxis /Assess for IRs
- o Administer pegloticase infusion, per site guidelines

Visit 10 (10 weeks)

- Obtain and record vital signs, including pulse rate, blood pressure, and body temperature
- Targeted physical exam
- Review / update concomitant medications
- Assess any AEs, and record
- Gout Flare Assessment
- Assess drug compliance (via pill count) and dispense course of MMF (1000 mg/twice per day) or PBO, with dosing instructions
- Laboratory Assessments
 - CBC with diff
 - CMP
 - sUA
 - Pregnancy test for premenopausal women
 - MMF adherence
- Gout Flare Prophylaxis
- o IR Prophylaxis /Assess for IRs
- o Administer pegloticase infusion, per site guidelines

Visit 11 (12 weeks)

- Obtain and record vital signs, including pulse rate, blood pressure, and body temperature
- o Review concomitant medications, and record
- Assess any AEs, and record
- Gout Flare Assessment
- o PROs (PROMIS-29 & GIS instrument)
- Assess drug compliance (via pill count)
- Physical Exam and detailed joint assessment
 - HEENT, and Neck
 - Cardiovascular
 - Respiratory
 - Gastrointestinal
 - Musculoskeletal
 - Neurologic
 - Integumentary
 - VS/Measurements
- Laboratory Assessments
 - CBC with diff
 - IgG
 - sUA
 - Pregnancy test for premenopausal women
 - CMP

- MMF adherence
- Pegloticase Antibody/Mechanistic Study
- o Gout Flare Prophylaxis
- o IR Prophylaxis / Assess for IRs
- Administer pegloticase infusion, per site guidelines

Following completion of Visit 11 participants will continue on pegloticase for an additional twelve weeks without immune modulating therapy to evaluate the longer term benefits of this approach. In Phase 2 participants will continue with pegloticase infusions every 2 weeks.

Visit 12 (14 weeks)

- o Obtain and record vital signs, including pulse rate, blood pressure, and body temperature
- Targeted Physical Exam and joint assessment
- o Review / update concomitant medications
- Assess any AEs, and record
- Gout Flare assessment
- Laboratory Assessments
 - CBC with diff
 - sUA
 - Pregnancy test for premenopausal women
 - CMP
- Gout Flare Prophylaxis
- IR Prophylaxis / Assess for IRs
- Administer pegloticase infusion, per site guidelines.

Visit 13 (16 weeks)

- Obtain and record vital signs, including pulse rate, blood pressure, and body temperature
- Targeted Physical Exam and joint assessment
- Review / update concomitant medications
- o Assess any AEs, and record
- Gout Flare Assessment
- PROs (PROMIS-29 & GIS instrument)
- Laboratory Assessments
 - CBC with diff
 - sUA
 - Pregnancy test for premenopausal women
 - CMP
- Gout Flare Prophylaxis
- o IR Prophylaxis / Assess for IRs
- Administer pegloticase infusion, per site guidelines

Visit 14 (18 weeks)

- Obtain and record vital signs, including pulse rate, blood pressure, and body temperature
- o Targeted Physical Exam and joint assessment
- Review concomitant medications, and record

- Assess any AEs, and record
- Gout Flare Assessment
- Laboratory Assessments
 - CBC with diff
 - SUA
 - Pregnancy test for premenopausal women
 - CMP
 - Pegloticase Antibody/Mechanistic Study
- Gout Flare Prophylaxis
- IR Prophylaxis /Assess for IRs
- Administer pegloticase infusion, per site guidelines

Visit 15 (20 weeks)

- o Obtain and record vital signs, including pulse rate, blood pressure, and body temperature
- o Targeted Physical Exam and joint assessment
- o Review concomitant medications, and record
- Assess any AEs, and record
- Gout Flare assessment
- o PROs (PROMIS-29 & GIS instrument)
- Laboratory Assessments
 - CBC with diff
 - sUA
 - Pregnancy test for premenopausal women
 - CMP
- Gout Flare Prophylaxis
- o IR Prophylaxis / Assess for IRs
- Administer pegloticase infusion, per site guidelines

Visit 16 (22 weeks)

- Obtain and record vital signs, including pulse rate, blood pressure, and body temperature
- Targeted Physical Exam and joint assessment
- o Review concomitant medications, and record
- Assess any AEs, and record
- Gout Flare assessment
- Laboratory Assessments
 - CBC with diff
 - sUA
 - Pregnancy test for premenopausal women
 - CMP
- Gout Flare Prophylaxis
- IR Prophylaxis /Assess for IRs
- o Administer pegloticase infusion, per site guidelines.

Visit 17 (24 weeks)

Participants will complete a final physical exam and update their medical history since enrollment.

- Obtain and record vital signs, including pulse rate, blood pressure, and body temperature
- Review concomitant medications, and record
- Assess any AEs, and record
- o PROs (PROMIS-29 & GIS instrument)
- Physical exam
 - HEENT, and Neck
 - Cardiovascular
 - Respiratory
 - Gastrointestinal
 - Musculoskeletal
 - Neurologic
 - Integumentary
 - VS/Measurements
- Laboratory Assessments
 - CBC with diff
 - sUA
 - Pregnancy test for premenopausal women
 - CMP
 - Pegloticase Antibody/Mechanistic Study

Following completion of Visit 17 participants will continue for an additional 12 weeks without pegloticase infusions for anti-pegloticase antibody testing. In Phase 3, participants will continue with blood draws and banking of biospecimen every 4 weeks.

Reminder: if a participant is discontinued from the study, they will move into long-term follow-up and will be asked to complete visits 17, in addition to the three 1-month visits 18-20.

Visit 18 (28 weeks)

Participants will report 4 weeks following completion of Visit 17 for a blood draw and banking of biospecimen for antipegloticase antibody testing.

Assessments

- Adverse events
- Pegloticase Antibody/Mechanistic Study

Visit 19 (32 weeks)

Participants will report 4 weeks following completion of Visit 18 for a blood draw and banking of biospecimen for antipegloticase antibody testing.

Assessments

- Adverse events
- Pegloticase Antibody/Mechanistic Study

Visit 20 (36 weeks-Final/visit)

Participants will report 4 weeks following completion of Visit 19 for a blood draw and banking of biospecimen for antipegloticase antibody testing.

Assessments

Adverse events

Pegloticase Antibody/Mechanistic Study

Unscheduled Visit

An unscheduled Visit will be conducted in the event of a suspected AE thought to be serious.

- Obtain and record vital signs, including pulse rate, blood pressure, and body temperature
- Review concomitant medications, and record
- Assess any AEs, and record
- Physical exam includes, but is not limited to
 - HEENT, and Neck
 - Cardiovascular
 - Respiratory
 - Gastrointestinal
 - Musculoskeletal
 - Neurologic
 - Integumentary
 - VS/Measurements
- Laboratory Assessments
 - CBC with diff
 - IgG
 - sUA
 - CMP
 - Pegloticase Antibody/Mechanistic Study

Follow-up

We will follow each participant from screening for up to six months until completion of the full study (week 36). If the study drug is discontinued, unless the subject withdraws consent, the subject will be followed for the full study period and all data will be collected as scheduled.

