8 STUDY INTERVENTION DISCONTINUATION AND PARTICIPANT DISCONTINUATION/WITHDRAWAL

8.1 DISCONTINUATION OF STUDY INTERVENTION

Due to the risk of anaphylaxis and IRs being higher in patients who have lost therapeutic response, participants with two consecutive serum urate levels above 6 mg/dL shall be classified as a non-responder and discontinued from the study. Investigators will obtain a pre-dose serum urate sample for all patients and review results to verify the serum urate level is \leq 6 mg/dL prior to infusion.

Discontinuation from the study intervention does not mean discontinuation from the study, and remaining study

procedures should be completed as indicated by the study protocol. If a clinically significant finding is identified (including, but not limited to changes from baseline) after enrollment, the investigator or qualified designee will determine if any change in participant management is needed. Any new clinically relevant finding will be reported as an adverse event (AE).

The data to be collected at the time of study intervention discontinuation will include the following: If the study drug is discontinued, unless the subject withdraws consent, the participant will complete visit 17 (two weeks post discontinuation) and visits 17-20. If the participant doesn't want to continue with the follow-up visit schedule detailed above, then it is important to complete a close-out visit.

Based on the known safety profiles of pegloticase and MMF and the procedures we have in place, we believe it is very unlikely, but possible that we could witness one serious AE related to infection. We will institute a stopping rule for safety re-evaluation that would occur if we register more than one such serious adverse reaction (eg. infection that leads to hospitalization). We would then stop the study to comprehensively review safety and our study protocols in conjunction with the DSMB. Other serious adverse reaction or deaths may or may not be related to the study and stopping or discontinuation of the study will be considered on an individual basis. See **Appendix 9** Data Safety Monitoring Plan.

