9.1 EFFICACY ASSESSMENTS

We will assess the feasibility and preliminary efficacy of MMF's ability to safely attenuate immunogenicity conferred by pegloticase as determined by the proportion of participants randomized to peg + MMF achieving and maintaining an $sUA \le to 6$ mg/dL through 12 weeks (Visit 11), compared to concurrent controls (peg + PBO). After 12 weeks of coadministration of MMF or PBO, all participants will continue on pegloticase for an additional 12 weeks without combination therapy to determine the durability of immune modulation by assessing the absolute change in sUA from baseline to Week 24 (Visit 17), change in sUA from Week 12 (Visit 11) to Week 24 (Visit 17), and to determine the proportion of participants with $sUA \le 6$ mg/dL through Week 24 (Visit 17), and Week 12 (Visit 11) to Week 24 (Visit 17). Samples will be drawn for laboratory assessment at Visits 1-17 and at unscheduled visits. At visits 18-20 specimen samples will be collected for assessment of anti-pegloticase antibodies.

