effect or pattern of response with anti-pegloticase Ab titers/types. This aim will be supported by analyses that compares the treatment groups using two group t-tests and regression analyses that include the time of the sampling (an offset) to adjust for any 12 or 24 week samples that may be taken earlier at the time of failure or dropout. Repeated measures assessments using all Ab data (both data points: baseline and last observation) will be assessed using random effects in PROC MIXED to assess the variability in response over time. Comparisons will be assessed using pre-specified contrasts. Analyses of the sUA will be similarly assessed using PROC MIXED with random effects for participant. In addition, addressing the secondary aim: b) determining the proportion of participants with sUA ≤ 6 mg/dL through 24 weeks, and Week 12 to Week 24; will be examined using Fisher's exact test. Continuous models estimating the areas under the dose-time curve with estimation based on using the trapezoidal rule will be constructed and adjusted for time under study yielding an average sUA during the observation period. These areas under the curve will be compared using similar linear models with an offset for the time under study. Exploratory analyses will assess association of covariates within group areas under the curve; 2) Identify and characterize the pegloticase immune response by immunoglobulin isotypes (IgG and IgM), specificities, and Ab titer.

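### Follow-up after stopping study drug is stated two ways, and on the short path most participants who stop have no Week 24 urate although Week 24 is defined as Visit 17

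*Combined protocol and SAP*

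**What the plan says.** **Full schedule.** The Follow-up paragraph at the end of Section 9 says that if study drug is stopped and consent is not withdrawn, "the subject will be followed for the full study period and all data will be collected as scheduled".

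**Short path.** Section 8.1 says that in the same situation "the participant will complete visit 17 (two weeks post discontinuation) and visits 17-20" (Visit 17 appears twice in that phrase). The reminder under Visit 17 in Section 9 says that a discontinued participant "will be asked to complete visits 17, in addition to the three 1-month visits 18-20".

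**Who is affected.** Section 8.1 states that "participants with two consecutive serum urate levels above 6 mg/dL shall be classified as a non-responder and discontinued from the study", and shortly afterwards that "Discontinuation from the study intervention does not mean discontinuation from the study".

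**Endpoint.** Section 9.1 describes durability as "assessing the absolute change in sUA from baseline to Week 24 (Visit 17" in the regular schedule, and gives a second change from Week 12 (Visit 11) to Week 24 (Visit 17). It adds that "At visits 18-20 specimen samples will be collected for assessment of anti-pegloticase antibodies". Neither Table 1 nor the visit lists in Section 9 show urate at Visits 18-20.

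**Analysis.** Section 10.4.3 compares continuous secondary outcomes by t-test or Wilcoxon test. It also proposes regressions with sampling time as an offset to "adjust for any 12 or 24 week samples that may be taken earlier at the time of failure or dropout", a mixed model for urate with random participant effects, and an area under the curve adjusted for time under study.

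**The concern.** The two rules produce different data. Under the full schedule, a participant who stops at Week 4 still has urate drawn at the true Week 24. Under the short path, the same participant's Visit 17 falls at about Week 6 and no urate is scheduled after it. Because Section 9.1 ties the Week 24 endpoints to the visit label, an analysis that follows the label would combine true Week 24 values from participants still on pegloticase with early post-stopping values from those who failed. Stopping depends on the outcome and is expected to differ between arms, so the comparison of urate change might not be like for like. PRO and antibody data labelled Visit 17 have the same timing problem.

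**Working it through.** **Planning rates.** Section 10.2 plans on 60% success in controls and 80% with MMF, with two-sided 5% type I error and 80% power. The usual formula with pooled variance and no continuity correction gives

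n = [1.96 × √(2 × 0.70 × 0.30) + 0.842 × √(0.60 × 0.40 + 0.80 × 0.20)]² / 0.20² = (1.270 + 0.532)² / 0.04 ≈ 81.2, rounded up to 82 per group.

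This matches the plan's figure, which is not in dispute. The rates are used below only to size the group that could be affected.

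**Visit timing on the short path.** Section 8.1 puts Visit 17 at stop week + 2. Section 9 spaces Visits 18, 19 and 20 four weeks apart, so they fall at stop week + 6, + 10 and + 14. I take the stop week to be the visit at which the second urate above 6 mg/dL is found.

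| Stop week | Actual week of Visit 17 | Weeks short of Week 24 | Actual weeks of Visits 18, 19, 20 (no urate) |
|---|---|---|---|
| 2 | 4 | 20 | 8, 12, 16 |
| 4 | 6 | 18 | 10, 14, 18 |
| 6 | 8 | 16 | 12, 16, 20 |
| 8 | 10 | 14 | 14, 18, 22 |
| 10 | 12 | 12 | 16, 20, 24 |
| 12 | 14 | 10 | 18, 22, 26 |
| 16 | 18 | 6 | 22, 26, 30 |
| 20 | 22 | 2 | 26, 30, 34 |
| 22 | 24 | 0 | 28, 32, 36 |

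**Baseline to Week 24.** A stop at Weeks 2-12 gives a last urate at Weeks 4-14. Only a stop at Week 22 gives a value at Week 24.

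**Week 12 to Week 24.** A stop before Week 10 leaves neither end of the interval: Visit 17 precedes Week 12 and there is no regular Visit 11. A stop at Week 10 gives a Week 12 value, labelled Visit 17, and nothing later. A stop at Week 12 has a start value, but the last urate is at Week 14.

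**Do the planned analyses close the gap?**
- The sampling-time offset takes account of when a sample was drawn but does not create a later one. It is described with the antibody and durability regressions, and no timing rule is given for the t-test or Wilcoxon comparison.
- The mixed model can yield a Week 24 mean only by relying on the course of participants still observed. The plan does not say whether time is entered as actual week or visit label.
- The time-adjusted area under the curve averages urate over each participant's own observation period, which is a different quantity from change to Week 24.
- The imputation example in Section 10.4.7 uses missed visits with observed values on both sides. An early stopper has no later urate.

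**Illustrative size.** Section 7.3 allocates 24 to MMF and 8 to placebo. If every planning-rate failure stopped early on the short path:
- MMF: (1 − 0.80) × 24 = 4.8
- placebo: (1 − 0.60) × 8 = 3.2
- total: 8.0 of 32, with proportions of 20% and 40%

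Using the 42% loss of efficacy quoted in Section 3.2 for controls gives 0.42 × 8 = 3.4 on placebo instead.

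**The case against.** The strongest reply has four parts.

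1. *No passage says that an early Visit 17 value is entered as Week 24.* A reader might infer that the plan openly does this. It does not: Section 9.1 links Week 24 to Visit 17 in the regular schedule. But Section 10.4.3 expects some 24-week samples to be taken at failure, and no rule separates visit label from actual week. The handling is unspecified, and following the label would produce the problem.

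2. *The consequences are limited.* This stands. The primary endpoint is fixed by Week 12, and Figure 4 uses only those success counts. Antibody evidence also enters the decision to proceed, but the plan does not tie that evidence to Visit 17. A participant with two consecutive values above 6 mg/dL has already failed the proportion maintained through Week 24. Section 10.4.3 calls the analyses descriptive.

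3. *The figure of 8 in 32 is not a forecast.* This also stands. Planning success rates are not stopping rates. One raised urate may fail the endpoint without triggering the two-consecutive rule, and participants who withdraw or are lost lack a Week 24 value under either follow-up rule. Under the full schedule, stopping alone would cost no Week 24 sample.

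4. *Bias has not been shown.* A reader might infer that the durability result is biased in a known direction. The documents do not support that: Section 3.2 describes a rapid rise in urate on loss of efficacy, but nothing shows how a value two weeks after stopping compares with one at Week 24.

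**Conclusion.** The contradiction is real and lies wholly in current text; it does not depend on the amendment history. If the short path is followed as written, participants who stop at Weeks 2-12 have a last urate 10 to 20 weeks before Week 24, and their Week 12 to Week 24 change may lack a valid start value, end value or both. It would be too strong to say that no participant who stops has a Week 24 urate, because a stop at Week 22 does. The affected endpoints are the two secondary urate changes and the Visit 17 PRO and antibody data. As an illustration, about 5 of 24 and 3 of 8 participants could be involved, assuming that every planning failure stops early and that the short path governs. Direction and size of bias remain unknown. The point warrants correction because it concerns the first-listed secondary objective, durability.

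**What to change.** 1. Reconcile Section 8.1, the reminder under Visit 17 and the Follow-up paragraph of Section 9 into one follow-up rule. Which rule to keep is for the investigators to decide. Under the full schedule, Visit 17 stays at Week 24 and the labelling problem disappears, apart from withdrawal and loss to follow-up.
2. If the short path is kept, label the post-stopping visit 'early termination', record its actual week, and do not enter it as Week 24 in the urate-change, PRO or antibody analyses. State that time in the mixed model and regressions is actual week.
3. State that participants who stop early for any reason count as not maintaining urate at or below 6 mg/dL through Week 24. This mainly settles stops for reasons other than raised urate.
4. Optionally, add a rank-based comparison over all mITT participants, with early failures ranked worst, as a sensitivity analysis to the planned Wilcoxon test. It should not replace absolute change, because it answers a different question.

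Measuring urate at Visits 18-20 would not close the gap: for stops before Week 10, even Visit 20 comes before Week 24.

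The cost is protocol and analysis-plan wording and one visit label with its date. Keeping the short path needs no new visits or assays; keeping the full schedule means carrying out the remaining scheduled visits for participants who stop.
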